### **6.3 Adverse Event Definition and Reporting Requirements**

#### **6.3.1 Adverse Events**

An AE is defined as any untoward medical occurrence in a clinical research participant administered an investigational product and which does not necessarily have a causal relationship with the investigational product. As such, an AE can be an unfavorable or unintended sign (including an abnormal laboratory finding, for example), symptom or disease temporally associated with the use of an investigational product, whether or not considered related to the product. The term “investigational product” for this study refers to the oral medication Truvada® (tenofovir disoproxil fumarate/emtricitabine).

Study participants will be provided instructions for contacting the study site to report any untoward medical occurrences they may experience, except for possible life-threatening events, for which they will be instructed to seek immediate emergency care. Where feasible and medically appropriate, participants will be encouraged to seek evaluation where a study clinician is based, and to request that the clinician be contacted upon their arrival. With appropriate permission of the participant, whenever possible, records from all non-study medical providers related to untoward medical occurrences will be obtained and required data elements will be recorded on study CRFs. All participants reporting an untoward medical occurrence will be followed clinically until the occurrence resolves (returns to baseline) or stabilizes.

Study site staff will document in source documents and the appropriate AE Log CRF all AEs reported by or observed in enrolled study participants regardless of severity and presumed relationship to study product. AE severity will be graded per the DAIDS Table for Grading Adult and Pediatric Adverse Events, Version 1.0, December 2004 (Clarification dated August 2009).

#### **6.3.2 Serious Adverse Event**

Serious adverse event (SAE) will be defined per U.S. Code of Federal Regulations (CFR) 312.32 and International Conference on Harmonization (ICH), “Good Clinical Practice: Consolidated Guidance” (E6) and “Clinical Safety Data Management: Definitions and Standards for Expedited Reporting” (E2A), as AE occurring at any dose that:

- Results in death
- Is life-threatening

- Results in persistent or significant disability/incapacity
- Is a congenital anomaly/birth defect
- Requires inpatient hospitalization or prolongation of existing hospitalization

This includes important medical events that may not be immediately life-threatening or result in death, or hospitalization but may jeopardize the patient or may require intervention to prevent one of the outcomes listed above.

Per ICH SAE definition, hospitalization itself is not an adverse event, but is an outcome of the event. The following types of hospitalization do not require expedited reporting to DAIDS:

- Any admission unrelated to an AE (e.g. for labor/delivery, cosmetic surgery, administrative, or social admission for temporary placement for lack of place to sleep)
- Protocol-specified admission (e.g. for procedure required by protocol)
- Admission for diagnosis or therapy of a condition that existed before receipt of study agent(s) and has not increased in severity or frequency as judged by the clinical investigator

### **6.3.3 Adverse Event Relationship to Study Product**

Relatedness is an assessment made by a study clinician of whether or not the event is related to the study agent. Degrees of relatedness will be categorized according to current DAIDS-approved guidelines.

### **6.3.4 Expedited Adverse Event Reporting**

#### **6.3.4.1 Adverse Event Reporting to DAIDS**

Requirements, definitions and methods for expedited reporting of Adverse Events (AEs) are outlined in Version 2.0 of the DAIDS EAE Manual, which is available on the RSC website at <http://rsc.tech-res.com/safetyandpharmacovigilance/>.

The DAIDS Adverse Experience Reporting System (DAERS), an internet-based reporting system must be used for expedited AE reporting to DAIDS. In the event of system outages or technical difficulties, expedited AEs may be submitted via the DAIDS EAE Form. For questions about DAERS, please contact DAIDS-ES at [[contact]](mailto:[contact]) or from within the DAERS application itself.

Sites where DAERS has not been implemented will submit expedited AEs by documenting the information on the current DAIDS EAE Form. This form is available on the RSC website: <http://rsc.tech-res.com/safetyandpharmacovigilance/>. For questions about EAE reporting, please contact the RSC ([[contact]](mailto:[contact])).

#### **6.3.4.2 Reporting Requirements for this Study**

The SAE Reporting Category, as defined in Version 2.0 of the DAIDS EAE Manual, will be used for this study.

The study agent for which expedited reporting is required is: Truvada® (tenofovir disoproxil fumarate / emtricitabine (TDF/FTC))

#### **6.3.4.3 Grading Severity of Events**

The Division of AIDS Table for Grading the Severity of Adult and Pediatric Adverse Events (DAIDS AE Grading Table) is should be used to grade adverse events and is available on the RSC website at <http://rsc.tech-res.com/safetyandpharmacovigilance/>.

#### **6.3.4.4 Expedited AE Reporting Period**

- The expedited AE reporting period for this study is as per the EAE manual.
- After the protocol-defined AE reporting period, unless otherwise noted, only SUSARs as defined in Version 2.0 of the EAE Manual will be reported to DAIDS if the study staff become aware of the events on a passive basis (from publicly available information).

#### **6.3.5 Pregnancy Outcomes**

Pregnancy outcomes will be collected for all study participants by contacting these women soon after anticipated parturition. After the participant's final study contact, any pregnancy outcomes that meet criteria for SAE reporting as described above (e.g., congenital anomalies) occurring among participants will continue to be expeditiously reported.

#### **6.3.6 Regulatory Requirements**

Information on all reported AEs will be included in reports to applicable regulatory authorities. The site IoR/designee will submit AE information in accordance with local regulatory agencies' or other local authorities' requirements. The site IoR/designee also will submit AE information and any other relevant safety information to the IRB in accordance with IRB requirements.

### **6.4 Social Harms**

In order to prevent adverse social events related to study participation, social harms will be monitored throughout the study. Social harms are any untoward social occurrences that happen

to a participant as a result of their participation in the study. Examples include loss of employment, harassment by neighbors, shunned by family, rejection by partner, etc. Although social harms due to this study are expected to be negligible, they will be monitored closely throughout the study. Information on social harms will be actively solicited from participants at follow-up visits and recorded on case report forms and captured in the study database. Participants will also be encouraged to report any social harm on an ad hoc basis when it occurs. In the event that a participant reports social harm, every effort will be made by study staff to provide appropriate care and counseling to the participant, and/or referral to appropriate resources for the safety of the participant as needed. Social harms that are judged by the Investigator of Record to be serious or unexpected will be reported to responsible site's IRB/EC at least annually, or according to their individual requirements. The nature and frequency of these social impact reports will be monitored by the protocol team on a regular basis. In addition, these data will be reviewed by the HPTN (SMC).

## **7.0 STATISTICAL CONSIDERATIONS**

### **7.1 Review of Study Design**

HPTN 066 is a Phase 1, multi-site, randomized, four-arm, open label study of TFV and FTC concentrations in various body compartments following oral Truvada® dosing under direct observation by the study team (directly observed therapy [DOT]) to assure 100% adherence to prescribed dosing regimen. The prescribed dosing regimens range from weekly to daily TDF/FTC (Truvada®) at one of two possible doses for a total duration of 5 weeks. Thirty two participants are sampled weekly for blood (serum and cells). At the end of the 5th week and 7th week, 16 of the 32 participants also undergo seminal fluid, rectosigmoid (tissue and luminal fluid) and vaginal sampling (tissue and luminal fluid). Samples are assayed for TFV, FTC and phosphorylated moieties of these drugs.

### **7.2 Endpoints**

#### **7.2.1 Primary Endpoints**

Consistent with the primary study objective, the following endpoint will be assessed on Day 28 and Day 35 across all 4 dosing arms:

- Concentrations of TFV and FTC in blood serum
- Concentrations of TFV-DP and FTC-TP in PBMCs and CD4+ blood cells

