**Table 1-1. Accumulation index for parent and phosphorylated moieties of TDF and FTC dosed either weekly (168 hours) or daily (24 hours).** Drug moieties and regimens are ranked by accumulation index. An index of 2 indicates a doubling of concentration at steady-state compared to a single dose. An index of 1 indicates no accumulation at steady-state. For example, the concentration observed with 100% adherence can look the same as no adherence if the non-adherent participant takes a single dose prior to the observed blood collection when TFV, FTC or TDF/FTC are used with prescribed weekly dosing regimens. By contrast, the concentration expected with 100% adherence to Truvada® will be 9.6 (TFV-DP) or 2.7 (FTC-TP) times the concentration observed if a participant has taken only a single dose prior to the scheduled observation. (Hawkins et al., 2005; Pruvost et al., 2005; Pruvost et al., 2009; Wang et al., 2004)

Drug moiety	Half-life (hours)	Dosing interval (hours, tau)	Dosing interval / half-life (tau/HL)	Accumulation index (Rac)
TFV-DP	150	24	0.2	9.5
FTC-TP	36	24	0.7	2.7
TFV-DP	150	168	1.1	1.9
TFV	17	24	1.4	1.6
FTC	10	24	2.4	1.2
FTC-TP	36	168	4.7	1.0
TFV	17	168	9.9	1.0
FTC	10	168	16.8	1.0

For this reason, TFV-DP (the intracellular form of TFV) is an excellent candidate for drug adherence monitoring, especially with daily dosing (Table 1-1). With an intracellular half-life of 150 hours, daily to weekly dosing of TDF has a TFV-DP accumulation index ranging from 9.5 to 1.9, offering a great range of sensitivity for determining reduced adherence over a large range of dose frequencies. In contrast, TFV concentration (measured in blood serum), when TDF is dosed daily, would be expected to perform much less well, with a small difference in drug accumulation at steady-state during daily dosing when compared to a single dose (e.g., taken on the day of observation). When using TDF on a weekly dosing regimen, there is no anticipated difference between drug concentrations of serum TFV compared to taking a single dose of TDF without any prior doses. Contrasting Figure 1-1 with Figure 1-2 illustrates this point graphically. The different dose regimens are easily distinguishable in Figure 1 where intracellular TFV-DP is measured. In contrast, the TFV serum levels are largely overlapping with daily and weekly dosing at least one day per week.

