## **2.0 STUDY OBJECTIVES AND DESIGN**

### **2.1 Primary Objectives**

The primary objectives of this study are to:

- Assess dose-proportionality of intracellular TFV-DP and FTC-TP from weekly to daily dosing (Arms 1-4).
- Describe intra-individual variability in intracellular TFV-DP and FTC-TP concentrations at steady-state (comparison of Day 28 and Day 35).

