### **2.3.2 Study Sampling**

Sampling will occur over 7 weeks: at enrollment (pre-dose), pre-dose #2 (Day 1 for treatment arm 4, Day 3 for treatment arms 2 and 3, and Day 7 for treatment arm 1) and Days 7, 14, 21, 28, 35 and 49 to support each of the several objectives as follows:

1. Sample blood serum and blood cells (total cells and CD4+ cells) weekly for 5 weeks (Enrollment and Days 7, 14, 21, 28, and 35) to assess rate of accumulation and dose-proportionality in concentrations of extracellular TFV and FTC and intracellular TFV-DP and FTC-TP.
2. Sample blood serum and blood cells at steady-state (Day 28 and Day 35) to assess intra-individual variability.
3. When participants consent to participate in HPTN 066, they will be offered the opportunity to participate in the intensive sampling cohort (to provide mucosal samples). The slots in the intensive sampling cohort will be balanced by gender, so that there will be two men and two women who will undergo mucosal sampling in each of the four arms of the study. Potential research participants who do not choose to participate in or are ineligible for the intensive sampling cohort will be offered participation in the non-intensive cohort. The study team will sample rectosigmoid, seminal and vaginal fluid, cells, and tissue (in addition to blood) at Days 35 and 49 to compare extracellular concentrations of TFV and FTC and intracellular concentrations of TFV-DP and FTC-TP, and to estimate the elimination rate of drug from these compartments.

The sampling described must occur on the days prescribed given the need to synchronize post-dose time (7 days) across the four regimens. The blood sampling time should precede the established dosing time by no more than one hour. If the participant cannot have tissue sampled as prescribed, sampling should take place within the visit window, described in the SSP. In all cases, there must be accurate recording of sample collection times.

Biopsies will not be performed during menstruation. As such, the timing of the first dose will need to take into consideration menstrual patterns and will be adjusted accordingly.

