## 5.0 STUDY PROCEDURES

An overview of the study visit and procedures schedule is presented in Appendix I. Presented below is additional information on visit-specific study procedures. Detailed instructions to guide and standardize all study procedures across sites will be provided in the SSP manual.

In addition to any Interim Visits that may occur in accordance with guidance outlined in Section 5.6, the following visits should take place for study participants:

- Screening
- Enrollment (first dosing day; Day 0)
- Pre-dose #2, Sample visit for single blood draw (accumulation index)
- Day 7, Non-Intensive Sampling visit
- Day 14, Non-Intensive Sampling visit
- Day 21, Non-Intensive Sampling visit
- Day 28, Non-Intensive Sampling visit
- Day 35, Non-Intensive plus Intensive \*† Sampling visit
- Day 49, Non-Intensive plus Intensive \*† Sampling visit, Termination Visit

\* Note: Sixteen of the total 32 participants will participate in the intensive sampling. The intensive sampling cohort will be divided evenly between men and women from each dosing cohort.

† Site staff will follow-up with participants via telephone, 24 hours after biopsy to inquire about any complications possibly resulting from the biopsy.

All sampling will occur no more than one hour prior to the scheduled dosing time.

As dosing will be observed by a study team member, participants will have up to daily contact with the study team. These will be termed “dosing visits” to distinguish them from study visits listed above.

Reimbursement for study visits will either take place at the end of each study visit, at the end of the study, or in a pro-rated manner, depending on site specific scheduling and IRB approvals.

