## **7.6 Data Analysis**

### **7.6.1 Primary Analyses**

#### **7.6.1.1 Dose Proportionality**

Dose proportionality will be assessed by a confidence interval approach based on the power model, using Day 35 pre-dose concentration ( $C_t$ ) data from all evaluable participants in Arms 1-4. Dose-proportionality will be declared if the 90% confidence interval of the slope completely falls in the critical interval ( $1 + \frac{\ln(0.5)}{\ln(7)} = 0.64, 1 + \frac{\ln(2)}{\ln(7)} = 1.36$ ). Analyte concentrations assessed for dose-proportionality will include TFV and FTC in fluids and their phosphorylated moieties, TFV-DP and FTC-TP, in cells. TFV-DP and FTC-TP will also be assessed in tissue homogenates. Weight-based or creatinine clearance-adjusted intracellular PK parameters may also be used in evaluating dose-proportionality (as well as secondary outcomes). Biological matrices included in the analysis will include: serum, PBMC, CD4+ blood cells, rectosigmoid and vaginal luminal fluid, semen, and rectosigmoid and vaginal tissue specimens (total tissue cells, CD4+ tissue cells, tissue homogenate) (see Table 7-3).

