### 7.6.1.2 Intra-Participant Variability

Intra-participant variability will be described by the coefficient of variation of concentrations assessed on Day 28 and Day 35, which are assumed to be at steady-state, using data from all evaluable participants across dosing arms. We will confirm that steady-state was achieved by evaluating drug concentration data from Day 7, 14, and 21. If the dose-proportionality is established as described earlier, then dose-adjusted concentrations will be used for a more robust assessment. These variability estimates will be calculated for all analytes in blood and blood cells. As supportive evidence, the accumulation data from Day 7, 14, and 21 will also be used to estimate the elimination rate constant. Tissue and luminal assessments cannot be calculated due to the absence of multiple steady-state samples.

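### Serum TFV and FTC are primary endpoints at pre-dose troughs where the protocol's own half-lives leave almost no FTC in the weekly arm, and possibly too little to measure for FTC in Arms 2-3 and TFV in Arm 1

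*Protocol*

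**What the plan says.** Protocol sections 2.3.3.1 and 7.2.1 give two groups of primary endpoints: "Concentrations of TFV and FTC in blood serum", and TFV-DP and FTC-TP in PBMCs and CD4+ blood cells. Section 7.2.1 adds that "the following endpoint will be assessed on Day 28 and Day 35 across all 4 dosing arms".

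The samples are troughs. Section 2.3.2 states that "The blood sampling time should precede the established dosing time by no more than one hour", and section 5.0 that "All sampling will occur no more than one hour prior to the scheduled dosing time".

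Two primary analyses then use the serum values. Section 7.6.1.1 fits the log-log power model to Day 35 pre-dose concentrations and declares proportionality if the 90% CI of the slope lies within 0.64 to 1.36. It states that "Analyte concentrations assessed for dose-proportionality will include TFV and FTC in fluids" and names serum among the matrices. Section 7.6.1.2 takes the Day 28/Day 35 coefficient of variation and says "These variability estimates will be calculated for all analytes in blood and blood cells".

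The primary objectives in section 2.1 do not mention serum. The first is to "Assess dose-proportionality of intracellular TFV-DP and FTC-TP from weekly to daily dosing (Arms 1-4"). The second describes intra-individual variability of the same two intracellular moieties.

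**The concern.** Serum TFV and FTC are cleared quickly compared with a weekly or twice-weekly interval. A sample taken just before the next dose therefore catches them at their lowest point, many half-lives after the last tablet. Section 1.1.7 comes close to saying so: "When using TDF on a weekly dosing regimen, there is no anticipated difference between drug concentrations of serum TFV compared to taking a single dose". It draws that conclusion only for detecting poor adherence, and the protocol never asks whether the pre-dose serum level is measurable.

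A concentration below the assay limit has no logarithm for the power model and no Day 28/35 CV. Three consequences follow for a result labelled primary:

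- If Arm 1 yields no values, the slope rests on weekly doses of 2 to 7, a 3.5-fold range, but is judged against limits built on ln(7).
- If only Arm 4 yields values, there is no slope.
- If a constant is substituted on both days, the CV is zero by construction.

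Endpoint rank, sampling time and both analyses are fixed in the protocol. A later rule for low values cannot restore what the sampling time removes.

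**Working it through.** **Inputs**
- Half-lives: TFV 17 h, FTC 10 h (Table 1-1).
- Accumulation formula: R = 1/(1 − e^(−kτ)), with k = ln 2/half-life (section 1.1.7).
- Time from last dose to the Day 28 or Day 35 trough: 168 h in Arm 1 and 24 h in Arm 4. In Arms 2 and 3 it is 96 h, because doses fall on Monday and Thursday (Figure 1-1 legend) and the second dose is on Day 3 (section 2.3.2). Doses in weeks 4 and 5 must be taken as scheduled (sections 4.5.2 and 7.3).
- Tablets per dose: one in Arms 1, 2 and 4, and two in Arm 3 (Table 4-1).
- Weekly dose ratios: 1, 2, 4, 7 (sections 1.2.2 and 7.3).
- Participants: 8 per arm.
- Assay limit and serum peak: not given.

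**The protocol's own figures first.** R for TFV is 1.602 at 24 h and 1.001 at 168 h. For FTC it is 1.234 and 1.000. Table 1-1 prints 1.6, 1.0, 1.2 and 1.0, and its other four rows also reproduce.

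**Trough in each arm.** Assuming mono-exponential decline, trough = tablets × sum over earlier doses of 2^(−hours since dose/half-life), in units of the level from one tablet. One unit is used for all arms because an assay limit is an absolute concentration.

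- TFV Arm 1: 2^(−168/17) = 0.00106, or 1/944.
- TFV Arm 2: 2^(−96/17) = 0.0200 from the last dose; adding 0.00106 from the dose before gives 0.021.
- FTC Arm 1: 2^(−16.8) = 0.00000876, or about 1/114,000.
- FTC Arm 2: 2^(−9.6) = 0.00129, or 1/776. Arm 3 is twice that, 1/388. Earlier doses raise both by less than 1%.
- Arm 4: TFV 0.376/(1 − 0.376) = 0.60; FTC 0.189/(1 − 0.189) = 0.23.

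| | Arm 1 | Arm 2 | Arm 3 | Arm 4 |
|---|---|---|---|---|
| TFV | 0.11% | 2.1% | 4.2% | 60% |
| FTC | 0.0009% | 0.13% | 0.26% | 23% |

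**Participants without a value.** Assume a limit between 1/100 and 1/5000 of a one-tablet level, and the Table 1-1 half-life for everyone.

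| Analyte | Limit | Unquantifiable |
|---|---|---|
| FTC | above about 1/388 | Arms 1-3: 24 of 32 |
| FTC | 1/776 to 1/388 | Arms 1-2: 16 of 32 |
| FTC | below 1/776 | Arm 1: 8 of 32 |
| TFV | above about 1/944 | Arm 1: 8 of 32 |
| TFV | below 1/944 | none |

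**Sensitivity to half-life.** For Arm 1 FTC to reach the limit, a participant would need a half-life of 168/log2(5000) = 13.7 h at the 1/5000 end, or 168/log2(100) = 25.3 h at the 1/100 end. For TFV in Arm 1, assumed half-lives of 25, 30 and 40 h give troughs of 0.95%, 2.1% and 5.4%.

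**If every value were measurable.** Relative to Arm 1, the TFV troughs are 1, 19.8, 39.7 and 568. The FTC troughs are 1, 148, 296 and about 26,700. Regressing the log of these on ln(1, 2, 4, 7) gives slopes of 3.0 and 4.8. Both lie outside 0.64 to 1.36 although the kinetics assumed are exactly linear. The trough reflects time since the last dose far more than the weekly dose.

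**The case against.** The strongest case on the other side has four parts.

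- **Serum was intended.** Section 1.2.1 says the study is meant to establish proportionality for serum as well as intracellular forms, and section 2.3.2 plans serum samples for both proportionality and variability. This stands: serum is no slip, and it should still be measured and reported. It does not explain primary rank, since section 2.1 leaves serum out.
- **The deciding figure is absent.** Without an assay limit or serum peak, nobody can show from the protocol that a given sample is unquantifiable, and half-lives differ between people. This also stands, and is why the counts are a range. TFV in Arm 1 is the most sensitive. FTC in Arm 1, at about 1/114,000, is not rescued at the stated 10 h anywhere in the assumed range.
- **Handling of low values belongs in the SAP.** True, and a missing rule is not the point here. Section 7.6.1.1 also already gives medians and interquartile ranges by arm, so part of a sensible serum summary is in place.
- **The effect is contained.** The sample size rests on TFV-DP, and the intracellular analyses do not use serum values. This limits the consequence to the serum results.

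A reader might infer that most participants will have no serum value, that Arms 2 and 3 are equally affected, or that both analytes fail. The documents do not support this. A majority is lost only for FTC, and only if the limit is above about 1/388. Arm 3's double dose puts its trough at twice that of Arm 2. At most 8 of 32 lose TFV.

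**Conclusion.** The point holds. Serum TFV and FTC are ranked primary without a matching primary objective, at a sampling time that cannot support the two analyses assigned to them in every arm.

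By strength:
- **Firm:** serum FTC in Arm 1 (8 participants), unquantifiable throughout the assumed range at the stated half-life.
- **Possible:** FTC in Arm 2, FTC in Arm 3 and TFV in Arm 1, depending on the assay limit.
- **Not affected by measurability:** TFV in Arms 2-4 and FTC in Arm 4.

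The proportionality rule fails for serum troughs whatever the assay limit, because linear kinetics alone give expected slopes of about 3.0 and 4.8. A failed declaration would say nothing about whether serum TFV or FTC is dose-proportional.

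The size rests on Table 1-1's half-lives, mono-exponential decline, the Monday/Thursday schedule and the assumed range for the limit. It would be too much to infer that the trial's primary conclusions are compromised: this check concerns serum only and does not judge the intracellular endpoints.

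**What to change.** - **Sections 2.3.3.1 and 7.2.1:** keep TFV-DP and FTC-TP in PBMCs and CD4+ blood cells as the primary endpoints, and move serum TFV and FTC to secondary. Sections 2.3.3.2 and 7.2.2 already list TFV and FTC in blood. Section 7.2.2 covers only Days 35 and 49, so Day 28 should be added for serum.
- **Section 7.6.1.1:** do not apply the 0.64 to 1.36 rule to serum troughs, quantifiable or not. Report percent quantifiable and median by arm.
- **Section 7.6.1.2:** compute the serum Day 28/35 CV by arm, and only in arms where nearly all values on both days are quantifiable.

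The cost is wording and the loss of a nominal primary claim on serum. Sampling, assays and the intracellular analysis do not change.
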